9.6 Risks and Anticipated Adverse Device Effects

No specific risks and anticipated device effects to be evaluated in the investigation. See section 19 for details on how AEs will be recorded and reported during the investigation.

	Clinical Investigation Code: KC09-108 Clinical Investigation Plan KCclin02	Revision: A
---	---	----------------

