7 JUSTIFICATION OF CLINICAL INVESTIGATION DESIGN

Before this clinical investigation, Previct Drugs has been evaluated in relevant pre-clinical testing and assessments. For a summary on the pre-clinical testing, please see the Investigators Brochure [16].

In parallel to this second clinical investigation a first-in-human early feasibility investigation in healthy volunteers is planned to be performed in the Netherlands.

This second pilot, explorative, early feasibility, pre-market clinical investigation aims to collect usability clinical data of Previct Drugs once used in the intended population (patients with SUD). In addition, it will also give valuable information on the feasibility of Previct Drugs function to measure pupils and eye movement and that it is safe to be used in the intended patient population. The clinical data collected is an important step in the product development of Previct Drugs as the data is required for continuing the development of the mathematical models for signal processing and algorithms for drug detection. The outcome will serve as a basis for finalizing the design of Previct Drugs after this investigation, and continuous studies in clinically significant settings prior to CE marking. For further details on the clinical research program, please see the Clinical Development Plan (CDP) available in the Clinical Evaluation Plan (CEP) [17].

An explorative design has been selected as it is a common approach when there is little or no experience of using a medical device in humans. This investigation is also an early feasibility study where the design of the medical device is not finalized, and the data collected as part of the investigation is required to complete the design.

The endpoints selected to be evaluated in this investigation, have been identified as proper ones to receive preliminary information on the usability of Previct Drugs.

In this study, patients with a known addiction will be studied from a usability perspective. It is important to collect eye data on patients with a substance use disorder. This population is also similar to the group of patients for which the product is intended to be used in the future.

It has been decided that at least one test with Previct Drugs is acceptable given the selected study population. The investigation is designed for three follow-up visits. The follow-up visits are optional for the study subject to complete within a time frame of four weeks after the baseline visit.

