8.2 Residual Risks and Anticipated Adverse Device Effects

During the risk analysis, hazards and hazardous situations associated with PreVict Drugs when used as intended, use errors and reasonably foreseeable misuse have been considered. Risks associated with body contact (mobile phone and computer keyboard) as related to biocompatibility and risks related to information security have also been considered and included.

In total, 47 risks were identified of which 40 are insignificant risks after mitigation and 7 risks that need to be further investigated during the product development of PreVict Drugs. No remaining risks are unacceptable after mitigation.

Risk controls have been implemented for all identified risks. There are no remaining risks which needs to be further investigated for risk reducing measures. The risks that were identified as unacceptable before risk mitigation measures were controlled to a satisfactory level and no additional risk control measures were deemed to be necessary. All defined risk control measures have been adequately implemented and verified as part of the testing activities during the product development phase.

The risks can be summarized into 18 different types of hazards, primarily relating to user error and function that could result in an incorrect measurement, erroneous value or false positive and in turn lead to a wrong or missed necessary patient treatment.

The different types of hazards are:

- Use error: knowledge-based failure (5)
- Use error: routine violation (8)
- Use error: rule based (4)
- Use error: related to IFU (2)
- Normal use patient shaking (1)
- Function (1)
- Function: incorrect input (2)
- Function: data transfer (5)
- Function: data loss (7)
- Function: incorrect input (2)
- Function: design (5)
- Information security (1)

	Clinical Investigation Code: KCC09-108 Clinical Investigation Plan KCClin02	Revision: A
---	--	----------------

- Leads to false security (1)
- Labeling loss (1)
- Biocompatibility: Chemical residues (1)
- Cyber security (1)

The identified hazards may lead to the following adverse events:

- Wrong or missed necessary treatment
- Eyes get irritated

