8.3 Risks Associated with Participating in the Clinical Investigation

Hazards and hazardous situations specifically associated with the study design, assessments, and population have been considered and evaluated. In total, 18 risks were identified of which 17 are insignificant risks after mitigation and 1 risk that need to be further investigated. No remaining risks are unacceptable after mitigation.

The risks can be summarized into 13 different types of hazards, primarily relating to function and usability in the investigation.

- Function: design (2)
- Function: incorrect input (1)
- Function: data loss (1)
- Function: data transfer (4)
- Pilot study not performed as planned (1)
- Pilot study not successful: (1)
- Use error: routine violation (2)
- Use error: rule based (1)
- Use error: knowledge-based failure (1)
- Study assessments: (1)
- Normal use subject shaking (1)
- Non-CE marked product available on the market (2)

During the clinical investigation there is a very small possibility that the identified hazards may lead to the following adverse events:

- Dizziness and/or nausea during test as eyes must be moved from one side to the other side.
- Dizziness and/or nausea during sampling with Breath Explore as several deep breaths for a few minutes is done.

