10.4 Safety Endpoint

The incidence and severity of adverse events associated with PreVict Drugs.

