Signal from any adverse event or device deficiency that indicates an imminent risk of death or a serious deterioration in the health in subjects, users, or other persons, and that requires prompt remedial action for other subjects, users, or other persons.

Note: This would include events that are of significant and unexpected nature such that they become alarming as a potential serious health hazard or possibility of multiple deaths occurring at short intervals.

Unanticipated Serious Adverse Device Effect (USADE)

Serious adverse device effect which by its nature, incidence, severity or outcome has not been identified in the current risk assessment.

Note: Anticipated Serious Adverse Device Effect (ASADE) is an effect which by its nature, incidence, severity or outcome has been identified in the risk assessment.

AEs will be documented as reported in the eCRF, without use of specific coding dictionaries.

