7.3.2 Presentation

AE/ADE:

The following summaries of AEs and SAEs will be given by for each medicinal product group and in total:

- Total number of AEs
- Total number of unique AEs
- Total number of unique, related AEs
- Total number (%) of subjects with at least one AE
- Total number (%) of subjects with at least one related AE
- Total number (%) which had AE as reason for premature discontinuation of IMD

Severity, action taken, concomitant therapy started, and subject outcome of the AEs will be given in data listings only. AEs, which were reason for premature discontinuation of IMD, will be listed separately.

The total number of SAEs and patients with a least one SAE will be given. Further summaries of SAEs depending on the number of SAEs observed.

SAE/SADE:

SAEs/SADEs, if any, will be listed only.

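### CIP 9.6 contradicts the safety endpoint and CIP 10.8.4 on anticipated device effects, and the SAP pre-specifies only a pooled related-AE percentage, with no breakdown by effect, no severity summary and no interval

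*Protocol*

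**What the plan says.** CIP section 8 names the effects that might occur. Section 8.2 lists "Eyes get irritated". Section 8.3 lists "Dizziness and/or nausea during test as eyes must be moved from one side to the other side" and, separately, "Dizziness and/or nausea during sampling with Breath Explore as several deep breaths for a few minutes is done". CIP 19.6 refers back to section 8 for potential AEs.

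CIP 9.6 then says "No specific risks and anticipated device effects to be evaluated in the investigation" and sends the reader to section 19 for how AEs are recorded.

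The safety endpoint in CIP 10.4 is "The incidence and severity of adverse events associated with PreVict Drugs". CIP 10.8.4 makes onset, severity, duration and frequency the safety measurement, covers both anticipated and unanticipated AEs, and includes causality. CIP 19.3.2 requires device-related and procedure-related AEs to be told apart.

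SAP 7.3 says "AEs will be documented as reported in the eCRF, without use of specific coding dictionaries". SAP 7.3.2 plans pooled counts, including "Total number (%) of subjects with at least one related AE", and puts severity in listings only. An AE listing is among the deliverables in SAP section 9. SAP 4.5 fixes the form of any confidence interval but does not call for one on safety data. SAP 7.1.2 does plan 95% intervals for the favourable usability answers.

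**The concern.** The CIP names a short list of plausible effects, makes the frequency and severity of anticipated AEs its safety measurement, and in 9.6 says anticipated device effects are not to be evaluated. A reader of the CIP cannot tell which statement governs, and the SAP does not settle it. No planned table shows how many subjects had eye irritation, dizziness or nausea, and no rule says how free-text terms would be grouped to obtain those counts.

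The single planned related-AE percentage also has an undefined referent. Dizziness from deep breathing during sampling and dizziness from the eye test could both fall into it, although only the second bears on the device endpoint.

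At stake is what the report can say about safety. CIP section 7 expects information "that it is safe to be used in the intended patient population". The CIP regards these effects as unlikely, so zero or very few events is a plausible result. In a study of this size, a bare 0% without an interval says less than it appears to say.

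**Working it through.** There is no figure in the plan to reproduce: neither document states a safety rate, a precision target or a calculated sample size.

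**Step 1. What the CIP asks for against what the SAP delivers**

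| Element | CIP | SAP 7.3.2 |
|---|---|---|
| Incidence of device-associated AEs | Endpoint, 10.4 | Pooled n (%) with a related AE; referent of related not stated |
| Severity | Endpoint, 10.4; measurement, 10.8.4 | Listings only |
| Anticipated effects | Frequency measured, 10.8.4; not evaluated, 9.6 | No table by effect; terms uncoded |
| Device versus procedure | To be distinguished, 19.3.2 | Not carried into the summaries |
| Precision | Not stated for safety | No interval planned |

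**Step 2. Inputs for the arithmetic**
- Subjects: 15 to 30 (CIP 10.6.4); SAP 3.3 gives up to 30.
- Outcome: one yes/no result per subject for a named effect.
- Interval: exact (Clopper-Pearson), two-sided 95%, matching the level and sidedness in SAP 4.5.

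**Step 3. Upper limit when no event is seen**

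Solve (1 − p)^n = 0.025, so p_U = 1 − 0.025^(1/n).
- n = 30: 1 − 0.025^(1/30) = 1 − 0.884 = 0.116, or 11.6%.
- n = 15: 1 − 0.025^(1/15) = 1 − 0.782 = 0.218, or 21.8%.

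A one-sided 95% limit, 1 − 0.05^(1/n), gives 9.5% and 18.1%. The message is the same.

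**Step 4. One or two events, same exact method**

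| Events | n = 30 | n = 15 |
|---|---|---|
| 1 | 3.3% (0.1 to 17.2%) | 6.7% (0.2 to 31.9%) |
| 2 | 6.7% (0.8 to 22.1%) | 13.3% (1.7 to 40.5%) |

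**Step 5. Chance of seeing an effect at all**

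P(at least one event) = 1 − (1 − p)^n. The documents give no true rate, so the values of p below are assumptions chosen to show a range.

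| Assumed true rate | n = 30 | n = 15 |
|---|---|---|
| 1% | 26% | 14% |
| 5% | 79% | 54% |
| 10% | 96% | 79% |

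For example, 1 − 0.95^30 = 0.785 and 1 − 0.95^15 = 0.537. At n = 15, an effect affecting one subject in twenty would be missed almost half the time.

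**The case against.** The strongest reply is that the endpoint concerns device-associated AEs as a whole, not each named effect, and that the planned related-AE percentage is an incidence of just that kind. This stands in part. A reader might infer that the safety objective gets no incidence at all, or that intercurrent illness is mixed into the only figure available. The documents do not support either: a related-AE percentage is planned, and events judged unrelated do not enter it. What the reply leaves open is whether related means device or procedure, and where severity is summarised.

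Second, 9.6 sits in the chapter on objectives and hypotheses and can be read as setting no particular risk as a target. On that reading anticipated effects are still collected under 10.8.4 and section 19. That is a fair reading of intent, and one should not infer that these events will go unrecorded. As worded, though, 9.6 says they are not to be evaluated, so the text still needs reconciling.

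Third, with at most 30 subjects and a full AE listing, counts by effect could be made by hand. True, but the grouping would then be decided after the data are seen.

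Fourth, intervals are optional in a descriptive pilot with no hypothesis and no pass/fail rule. That limits the severity of the point. It does not explain why favourable usability answers get 95% intervals and safety percentages do not.

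One might also infer that free-text variants of one complaint would count as different unique AEs. The SAP does not define unique. CIP 19.3.1 keeps one identifier when severity changes, so counting by identifier is at least as plausible.

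**Conclusion.** The point holds as a contradiction within the CIP and a gap in the SAP's safety presentation. CIP 9.6 conflicts with 10.4 and 10.8.4. The SAP covers the incidence part of the endpoint only through a pooled percentage whose referent is undefined, and it summarises neither severity nor any of the effects named in section 8.

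The numerical consequence is that zero events leaves a true incidence of up to 11.6% at n = 30 or 21.8% at n = 15 compatible with the data. This assumes independent subjects, one result per subject pooled over the visits attended (one to four), and every subject in the denominator. A smaller denominator widens the limits.

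It would go too far to say that the CIP expects these effects: it calls eye irritation low or non-existent in risk and dizziness or nausea a very small possibility. Nor are all of them device effects, since one dizziness/nausea item arises from breath sampling. The severity is minor. Nothing here invalidates the study, but the correction is cheap and changes what a zero count can be said to show.

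**What to change.** 1. **CIP 9.6:** reword it so that it agrees with 10.4 and 10.8.4, stating that the section 8 effects are evaluated descriptively as part of the safety endpoint.
2. **SAP 7.3.2:** add one table of subjects (n, %, exact two-sided 95% interval) with eye irritation, dizziness, nausea and other AEs, split by relation to device or procedure and by severity grade. Because breath sampling is voluntary (CIP 10.8.2), show the number of subjects sampled alongside the sampling-related counts.
3. **Grouping rule:** assign verbatim terms to these rows before database lock and keep the mapping with the listing. No coding dictionary is needed.
4. **Reporting rule:** where a row has no events, give the upper limit in the safety conclusion, not a bare 0%.

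Keep the non-leading elicitation in CIP 19.3 and add no symptom checklist. The table uses items already recorded for each AE (description, severity, and causality for device and procedure), so no new data collection is required.

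The cost is one extra table, a short grouping exercise and a CIP wording change handled under CIP section 14. That change may need notification to, or approval by, the ethics committee and authority. The downside for the sponsor is a less favourable safety statement when no events are seen.

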10 DESIGN OF THE CLINICAL INVESTIGATION

10.1 General

This will be a pre-market, explorative, early feasibility, pilot, controlled clinical investigation designed to collect initial clinical data for PreVict Drugs. The clinical data collected in this early feasibility study together with the data from the KCclin01 investigation, is an important step in the product development of PreVict Drugs as the data is required for evaluating the usability and continuing the development of the mathematical models and algorithms for drug detection.

This investigation will give valuable information on the usability of PreVict Drugs once being used in patients with confirmed SUD according to the definition in the CIP. In addition, it will also give valuable information on the feasibility of PreVict drugs function to measure pupils and eye movements.

Potential study subjects interested to participate in this investigation will be provided with verbally and written information about the investigation. Each potential subject will be provided with the subject information sheet that explains the investigation, procedures, risks, and benefits. If a subject thereafter consents to participate, the informed consent will be signed and dated by the subject and the investigator who provided the information. The investigation will continue with screening and baseline collection to confirm eligibility. Relevant baseline data will be collected including first measurements with PreVict Drugs at the site. The follow-up visits are optional but up to three visits can be scheduled within a period of four weeks after the baseline visit. Four weeks after the baseline visit, the subject will be terminated from the study, even if no follow-up visit was made. It is also possible that all clinic visits are completed faster than the study timeline of four weeks.

The clinical investigation procedures are further explained in section 10.8.

The overall duration of the clinical investigation is anticipated to be approximately 3 months, including two months enrolment period.

No comparator will be used in this investigation as it is an early feasibility study to collect initial data on PreVict Drugs.

10.2 Primary Endpoint

- Observation of a study subject during a test with PreVict Drugs through answering the following 18 usability questions:
 1. Please evaluate the study subject's ability to use the mobile phone?
 2. How did you perceive the study subject's ability to follow the instructions given by PreVict Drugs?
 3. If you experienced that the study subject had difficulties, please select the suitable choice/choices below.
 4. How did the study subject experience to put him/herself in the right position to be able to start a test?
 5. If you experienced that the study subject had any difficulty, please select the suitable choice/choices below.
 6. How would you evaluate the study subject's ability to perform a Cross-eyes test?
 7. If you experienced that the study subject had difficulties, please describe:

	Clinical Investigation Code: KC09-108 Clinical Investigation Plan KCclin02	Revision: A
---	---	----------------

8. How would you evaluate the study subject's ability to perform a Nystagmus test?
9. If you experienced that the study subject had difficulties, please describe:
10. How would you evaluate the study subject's ability to perform a Contraction Test?
11. If you experienced that the study subject had difficulties, please describe:
12. How did the study subject experience keeping the phone still during the test?
13. If the study subject had difficulties, please select the suitable choice/choices below.
14. In addition to the basic instructions, did the study subject need additional support performing tests with PreVict Drugs?

If No, please forward to question no. 17.

15. What type of additional support did the study subject need? Please select the suitable choice/choices below.
16. Was the study subject able to perform the test after receiving additional support?
17. How many efforts did it take the study subject to perform test with PreVict Drugs?
18. How likely do you think it is that the study subject will be able to perform tests with PreVict Drugs without assistance in a home environment?

10.3 Secondary Endpoint(s)

- The fraction of collected pupillometry data from the mobile phone application, which can be transformed into pre-defined key features using native pupillograms.
- The fraction of collected pupillometry data from the mobile phone application, which can be transformed into pre-defined key features using refined pupillograms and key feature extraction algorithms.

10.4 Safety Endpoint

The incidence and severity of adverse events associated with PreVict Drugs.

10.5 Investigational Device

The subject will perform two sets of eye measurement tests with PreVict Drugs at the first and follow-up visits (if follow-up visits are performed). Each eye measurement set consists of four tests:

- 1 Cross-eyes test
- 1 Nystagmus test
- 2 Contraction tests at 2 different light conditions

	Clinical Investigation Code: KC09-108 Clinical Investigation Plan KCclin02	Revision: A
---	---	----------------

10.6 Subjects

10.6.1 Inclusion Criteria

The subjects have to meet all of the following criteria to be eligible to participate the investigation:

1. Signed Informed Consent Form
2. Male and female
3. A recurrent visitor at Sprututbytesprogrammet in Uppsala defined as visited the clinic within the last 3 months
4. SUD in accordance with DSM-5 criteria according to investigator/designee judgement
5. Age 18 years and older
6. Negative urine pregnancy test for all fertile women
7. Been informed of the nature, the scope, and the relevance of the clinical investigation
8. Voluntarily agreed to participation and has duly signed the Informed Consent Form

10.6.2 Exclusion Criteria

Subjects meeting any of the following criteria will not be permitted to participate in the investigation:

1. Participating in another clinical investigation which may affect the study outcome according to clinical judgement
2. Pregnancy or lactating
3. Blind
4. Deaf
5. Any ECG dangerous arrhythmia according to the investigator or designee judgment
6. Any disease or condition that may influence pupillary reflexes based on clinical judgement
7. Undergone eye surgery that may influence pupillary reflexes based on clinical judgement
8. Not able to read or understand the local language
9. Any planned travel or treatment which will make it impossible to participate according to the investigator or designee
10. Any other condition that as judged by the investigator may make the follow-up or investigation appropriate
11. That according to the Declaration of Helsinki is deemed unsuitable for study enrolment

10.6.3 Relationship of Investigation Population to Target Population

In this early feasibility investigation of PreVict Drugs, it has been decided to use patients with SUD according to the definition in the CIP to collect usability data. The assumed intended population for PreVict Drugs that will be CE-marked is patients diagnosed with SUD where PreVict Drugs will be used to aid individualized treatment and follow-up of patients undergoing treatment for SUD. The data collected in this investigation will thereby be collected from a very similar population PreVict Drugs is intended to be used for.

Data from PreVict Drugs measurements will also be collected from this population, which will provide valuable input for continued development of the mathematical models and algorithms for drug detection with PreVict Drugs after the investigation is completed.

